### ***Handling of missing screening value to derive actual randomization strata***

In case of missing data at screening visit for HbA1c and BMI, unscheduled data before randomization visit can be used. If the sample is confirmed as being for the purpose of a re-screen, then the result is sent to be integrated into IRT. In case of several data collected, the earliest is used.

### **2.5.4 Windows for time points**

Nominal post-baseline visits will be used for descriptive statistics and time course plots.

### ***Display of safety data by visit (laboratory variables and vital signs)***

Descriptive statistics (N, mean, SD, minimum, median, maximum) of quantitative laboratory variables and vital signs (observed data and change from baseline) during the on-treatment period for all scheduled visits as per protocol will be provided (ie, only including participants having non-missing assessments at a nominal visit). Summaries showing data by visit will be presented according to the visit number and labeled with the targeted approximate day/week.

As specified in the study protocol, laboratory data from scheduled visits are reported by central laboratories. When both central and local laboratories report values from the same blood sample (ie, sample collected at the same date and time), only measurements from the central laboratory will be included in the analyses. When only local laboratory results are reported and central laboratory results are unavailable, the local results will not be used in the efficacy analyses. In the safety analyses, local results will only be used in the PCSA summary if they are accompanied by a local laboratory normal range.

When a participant has more than 1 measurement from the central laboratory for the same laboratory parameter on the same date, the average of the measurements will be used. For the same laboratory parameter, if a participant has more than one measurement on different dates for the same scheduled visit, the value closest to the scheduled visit will be used for the scheduled visit. When the values for the same scheduled visit are equidistant, the last value should be used for the scheduled visit.

### ***Early Treatment Discontinuation (efficacy parameters)***

Subjects who discontinue treatment at or just before a regularly scheduled visit will have the Early Treat Term Visit page completed instead of the scheduled visit in the eCRF, and the scheduled visit will be reported as not done. For analysis purposes, values from Early Treat Term Visits will be mapped directly to the scheduled visit.

### ***Efficacy data at Week 30 / Week 56***

The scheduled measurements at the endpoint visit (Week 30 or Week 56) as collected will be used in the efficacy analyses including those obtained after IMP discontinuation and/or introduction of rescue therapy. For participants whose efficacy measurement is not available at the endpoint visit, the measurement at unscheduled visit (including the end of treatment and/or study visit for those prematurely discontinued) will be used if the unscheduled measurement is within +/-30 days (7 days for FPG and SMPG) of the date of the end point visit [targeted study Day 210 for Week 30 (or Day 392 for Week 56)]. If multiple measurements are associated to the same targeted date, the closest to the targeted study day will be used. In case of equality, the last measurement will be used. If there are still no measurements for a given parameter at an endpoint visit, the data is considered missing for efficacy analyses, where multiple imputation would be applied as appropriately as described in [Section 2.4.4.1](#).

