#### 8.1.2 Fasting plasma glucose

Plasma glucose will be assessed in a fasted state (as defined in [Section 5.3.1](#)) according to the schedule detailed in the SoA ([Section 1.3](#)). If participant is not fasting at the time of the visit, a re-test should be scheduled in a fasting state for the next day (or as soon as possible). For the efficacy assessments of the study, FPG is measured at a central laboratory.

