## 2 STATISTICAL AND ANALYTICAL PROCEDURES

### 2.1 ANALYSIS ENDPOINTS

#### 2.1.1 Demographic and Baseline characteristics

The Baseline value (except for serum creatinine and eGFR) is defined as the last available value prior to the first dose administration of open-label IMP or the last available value on or before the date of randomization if not treated with the open-label IMP. Note: any assessment undertaken on the day of first dose administration of open-label IMP with missing assessment time will be considered as Baseline.

For serum creatinine and eGFR, baseline is defined as the average of all values before the first dose of the open-label IMP for those randomized and exposed or before randomization for those who were randomized but never exposed to open-label IMP.

All Baseline safety parameters (apart from those listed below) are presented along with the on-treatment summary statistics in the safety sections ([Section 2.4.5](#)).

Summary statistics of baseline efficacy parameters by treatment group and overall will be provided in randomized population.

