#### **2.1.4.3 Laboratory safety variables**

Clinical laboratory data consists of blood analysis, including hematology, clinical chemistry and urinalysis. Clinical laboratory values will be summarized in both standard international units and conventional units (US) when applicable.

Blood samples for clinical laboratories will be collected at designated visits (see Schedule of Activities in [Appendix D](#)). The following laboratory parameters will be measured at central laboratory:

- Hematology
  - Red blood cells and platelets: Platelet count, Red blood cell count, Hemoglobin, Hematocrit;
  - White blood cells: White blood cell count, differential count (Neutrophils, Lymphocytes, Monocytes, Eosinophils, Basophils).
- Clinical chemistry
  - Pancreatic enzymes: Amylase, Lipase;
  - Electrolytes: Potassium, Sodium;
  - Renal function: Creatinine, Estimated glomerular filtration rate (MDRD formula);
  - Liver function: Alanine aminotransferase (ALT), Aspartate aminotransferase (AST), Alkaline phosphatase (ALP), Total bilirubin.
  - Lipid profile: Triglyceride, Total cholesterol, Low-density lipoprotein cholesterol, High-density lipoprotein cholesterol

For triglycerides, only values assessed in fasted patients will be analyzed.

  - Calcitonin

Technical formulas are described in [Section 2.5.1](#).

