#### **2.5.2 Data handling conventions for secondary efficacy variables**

No special data handling.

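### The Week 30 and Week 56 FPG selection rule has no fasting criterion, so read literally it can prefer a non-fasting glucose to the fasting re-test

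*SAP*

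**What the plan says.** Protocol 8.1.2 requires plasma glucose to be assessed fasted, and protocol 5.3.1 defines the overnight fast for Visits 3, 6, 7, 10, 12 and 14. Protocol 8.1.2 also provides for participants who attend unfasted: "If participant is not fasting at the time of the visit, a re-test should be scheduled in a fasting state for the next day". The same sentence allows a later date when that cannot be done.

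SAP 2.5.4 then sets the selection order for Weeks 30 and 56:

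- First choice: "The scheduled measurements at the endpoint visit (Week 30 or Week 56) as collected will be used in the efficacy analyses".
- Fallback: "For participants whose efficacy measurement is not available at the endpoint visit, the measurement at unscheduled visit". The condition on timing is that such a value "will be used if the unscheduled measurement is within +/-30 days (7 days for FPG and SMPG) of the date of the end point visit".
- Tie-break: "If multiple measurements are associated to the same targeted date, the closest to the targeted study day will be used"; if still equal, the last one.
- Otherwise the value is missing and goes to multiple imputation.

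SAP 2.5.2, on secondary efficacy variables, says only "No special data handling". The one fasting filter in the SAP is in 2.1.4.3: "For triglycerides, only values assessed in fasted patients will be analyzed".

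Change in FPG to Week 56 is a secondary endpoint, tested for superiority at steps 7 (6 mg) and 8 (4 mg) in SAP 2.4.4.3. FPG at Week 30 and the C-peptide/FPG ratio are exploratory.

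**The concern.** The protocol foresees that some participants will arrive unfasted and arranges a fasting re-test so that a valid value exists. The SAP rule that decides which value is analysed does not ask whether a value was fasted. It ranks values by visit label, then by calendar distance, then by recency. A programmer following that order has no instruction to prefer the re-test.

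A reported FPG may well be unfasted. Protocol 6.1.2.2 asks the investigator, after a high confirmatory FPG, to check that the sample was taken fasting. Protocol 6.3.1 masks post-baseline FPG to investigators, so sites cannot pick out a doubtful value by its size.

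The contrast with triglycerides matters. The lipid profile is scheduled at baseline, Week 30 and Week 56, which are visits where FPG is also drawn. The SAP therefore filters one analyte on fasting status at those visits and leaves the formally tested one unfiltered. At stake are the precision of the FPG comparison, its freedom from bias if unfasted attendance differs by arm, and whether two programmers would build the same dataset.

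**Working it through.** **1. The plan's own figure.** SAP 1.3 gives 91% power for HbA1c noninferiority: 300 per arm, SD 1.1%, margin 0.3%, true difference 0, 1-sided alpha 0.025. SE = 1.1 × √(2/300) = 0.0898; 0.3/0.0898 = 3.34; 3.34 − 1.96 = 1.38; Φ(1.38) = 0.916. The figure is reproduced. FPG does not enter it, so nothing below changes it.

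**2. Which value is selected at Week 56.** The schedule of activities allows the visit on Day 392 ± 5, so on Days 387 to 397 (11 days). Suppose a non-fasting glucose is reported on day v and a fasting re-test on day v + k. Three readings of SAP 2.5.4 are open:

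- A: the scheduled value always takes precedence.
- B: both values are coded to the visit; the one closest to Day 392 is used, ties going to the last. The re-test is used if |v + k − 392| ≤ |v − 392|.
- C: a non-fasting glucose is not an available FPG. The re-test is used if |v + k − 392| ≤ 7.

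| Re-test delay k | A | B | C |
|---|---|---|---|
| 1 day | 0 of 11 | 5 of 11 | 11 of 11 |
| 2 days | 0 of 11 | 5 of 11 | 11 of 11 |
| 3 days | 0 of 11 | 4 of 11 | 10 of 11 |
| 7 days | 0 of 11 | 2 of 11 | 6 of 11 |

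Under B with k = 1, the re-test is chosen for visits on Days 387 to 391 and the non-fasting value for visits on Days 392 to 397. The calendar decides, not the fast. Only C gives what protocol 8.1.2 intends, and the SAP does not state C.

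**3. Size.** The documents give no FPG SD, no expected FPG difference, no unfasted share and no size of the excess. Assumed here: SD of change 2.5 mmol/L, true difference 0.6 mmol/L, share unfasted p from 1% to 10%, excess D from 2 to 4 mmol/L, unfasted attendance unrelated to the true change, 300 per arm.

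- Shift in an arm mean = p × D: from 0.01 × 2 = 0.02 to 0.10 × 4 = 0.40 mmol/L.
- Added variance = p(1 − p)D². At p = 5%, D = 3: 0.4275, and 0.4275/6.25 = 7%. At p = 2%, D = 2: 0.0784/6.25 = 1%. At p = 10%, D = 4: 1.44/6.25 = 23%.
- SE of a difference without contamination = 2.5 × √(2/300) = 0.204 mmol/L; power = Φ(0.6/0.204 − 1.96) = 0.836.
- Arms equally affected, p = 1%, D = 2: SD = √(6.25 + 0.0396) = 2.508, power 0.834.
- Arms equally affected, p = 10%, D = 4: SD = √(6.25 + 1.44) = 2.773, power 0.755.
- Only one arm affected: the bias equals the shift, 0.02 to 0.40 mmol/L. In general it is the difference in p between arms times D.

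**The case against.** The strongest reply is that FPG means fasting plasma glucose. On the protocol's definition a non-fasting result is not an FPG, so the measurement is not available and the 7-day fallback admits the re-test. That is reading C, and it is a fair one. The SAP does not state it, however, and the explicit triglyceride filter shows that its authors wrote fasting conditions down where they meant them to be programmed.

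A reader might go further and infer that the SAP has non-fasting glucose analysed as FPG and throws the re-test away. The documents do not support that. No section says so. It would require that a non-fasting sample is drawn and reported, that it counts as available, and that the re-test is coded as unscheduled, and none of these is stated. In context, *as collected* refers to keeping values obtained after treatment discontinuation or rescue, not to fasting state. Nor does SAP 2.5.2 rule out FPG handling, since 2.5.4 itself sets a special 7-day window for FPG. Protocol 8.1.2 says only that a re-test should be scheduled, so a valid value cannot be assumed to exist in every case.

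The objections on size also stand. The inputs are assumptions, a shift common to the arms cancels, and nothing in the documents suggests that unfasted attendance differs by arm. FPG occupies the last two steps of the sequence.

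A reader might also want non-fasting baseline values removed. That does not work. Baseline is the "last available value prior to the first dose administration of open-label IMP", and FPG is first scheduled at Visit 3, where the first injection is given. A re-test after that injection cannot serve as baseline, and SAP 2.4.4.1 would replace a missing baseline needed for imputation by the population mean. Likewise, the re-test in protocol 8.1.2 covers plasma glucose only, so no C-peptide re-test can be presumed.

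**Conclusion.** The point holds as a gap in a stated selection rule. Read literally, SAP 2.5.4 can choose a non-fasting glucose over the fasting re-test for a formally tested secondary endpoint, and the plausible readings use a next-day re-test on 0, 5 or 11 of the 11 permitted visit days.

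The main expected effect is lost precision: a variance increase of about 7% in a middle case (5% unfasted, 3 mmol/L high), with power between 0.834 and 0.755 against 0.836 over the assumed range. Bias follows only if unfasted attendance differs between arms. All these sizes rest on the assumed SD, difference, share and excess and on the planned 300 per arm; the smaller modified ITT set that SAP 2.3.1.2 introduces would raise every SE. The HbA1c endpoint and the 91% power are unaffected. The change is worth making because it is cheap and brings the SAP into line with protocol 8.1.2, not because the FPG result is shown to be wrong.

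**What to change.** Before database lock, add to SAP 2.5.4, with a pointer from 2.5.2: only fasted central-laboratory values qualify as FPG at Weeks 30 and 56; a value recorded as non-fasting counts as not available; the fasting re-test within the existing 7-day window is used instead, whether coded to the visit or as unscheduled; otherwise the value is missing and imputed as planned.

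For the exploratory C-peptide/FPG ratio, use only samples in which both analytes were fasted, without assuming a C-peptide re-test. At baseline, keep non-fasting values in the main FPG analysis, flag them, and check their influence in a sensitivity analysis.

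Cost: one sentence and one filter on fasting status, which the triglyceride rule already presupposes. The downside is that a few non-fasting endpoint values without a usable re-test become missing. Under SAP 2.4.4.2.2 and 2.4.4.1 these are imputed around the participant's own baseline, so on average as no change, which is itself a distortion. The number of such replacements per arm should be reported.

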#### **2.3.1.2 Modified Intent-to-treat population**

Due to the study terminated early by sponsor on September 9, 2020 (hereinafter referred to as “early termination”), the efficacy analyses will be performed in mITT population instead of ITT population originally planned. The mITT population is defined as,

- Participants who have completed the study treatment, or
- Participants who discontinued the study treatment AND completed/discontinued the study before the early termination, or
- Participants who discontinued treatment before early termination and discontinued the study due to early termination within 30 days of the target Week 56 visit (Day 392), or
- Participants who discontinued treatment due to early termination within 30 days of the target Week 56 visit (Day 392).

Participants will not be included in mITT if they discontinued study due to termination and discontinued study treatment (before or due to early termination) and had visits performed more than 30 days before the target Week 56 visit (Day 392).

By-visit summary will be provided for ITT population in addition for mITT population.

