## **2.4.4 Analyses of efficacy endpoints**

Efficacy analyses will be performed on the ITT population using efficacy assessment collected during the study, including those obtained after IMP discontinuation and/or introduction of rescue therapy, unless otherwise specified (see [Section 2.5.4](#)).

Due to COVID-19 pandemic, participants may not be able to maintain their regular clinical visits according to the study protocol, with the closure of facilities, safety concern for the participants to go to the sites, unavailability of the investigators for treating participants, interruption of transportation or other COVID-19 related reasons. Data missingness due to these reasons is likely to be missing at random. For a continuous endpoint, all observed data of participants within the same treatment group can be used for imputation in an MAR approach. Sensitivity analyses will be performed to take into consideration of the impact of COVID-19 if the number of participants with missing endpoint data due to COVID-19 is above the threshold as specified in the following sections.

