#### **2.4.4.2.2 Changes in FPG from Baseline to Week 56 and in body weight from baseline to Week 56**

Changes in FPG from baseline to Week 56 and in body weight to Week 56 will each be analyzed using the same ANCOVA model with missing values imputed by MI analysis method as the method used for the primary efficacy endpoint analysis. Differences between treatment groups and CIs will be estimated by this method. The least squares (LS) means, standard errors of LS means within each treatment group and the adjusted mean and associated two-sided 95% CI of the difference between efpeglenatide 4, 6 mg and 1.5 mg dulaglutide group will be presented.

Summary statistics at protocol scheduled visits and for the last on-treatment value will also be provided for FPG and body weight.

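### Under the SAP 2.5.4 window, mITT participants stopped by the termination with an end-of-treatment visit on Days 362 to 384 keep their HbA1c and weight, but their measured FPG is replaced by a draw around baseline

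*SAP*

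**What the plan says.** **Who is analysed.** After the sponsor stopped the study on 9 September 2020, SAP 2.3.1.2 states that "the efficacy analyses will be performed in mITT population instead of ITT population originally planned". The fourth bullet of the mITT definition admits "Participants who discontinued treatment due to early termination within 30 days of the target Week 56 visit (Day 392". SAP 2.4.4 still reads "Efficacy analyses will be performed on the ITT population using efficacy assessment collected during the study", so the two sections disagree on the population.

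**What is measured.** Footnote a of the schedule of activities (SAP Appendix D) asks for a visit soon after the last dose, with the assessments planned for the end-of-treatment visit. The schedule shows that these include FPG.

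**Which value counts as Week 56.** SAP 2.5.4, in the paragraph on efficacy data at Week 30 and Week 56, says that if the scheduled value is absent, "the measurement at unscheduled visit (including the end of treatment and/or study visit for those prematurely discontinued) will be used", provided it falls "within +/-30 days (7 days for FPG and SMPG) of the date of the end point visit". Failing that, "the data is considered missing for efficacy analyses, where multiple imputation would be applied as appropriately as described in" SAP 2.4.4.1.

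**How missing FPG is filled.** SAP 2.4.4.2.2 gives FPG the "same ANCOVA model with missing values imputed by MI analysis method as the method used for the primary efficacy endpoint analysis". SAP 2.4.4.1 defines that method as a normal draw whose mean is the participant's own baseline.

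**A second rule.** The preceding paragraph of SAP 2.5.4, on early treatment discontinuation, maps early-termination visit values to the scheduled visit when treatment stops at that visit or *just before* it. It gives no day limit and no order of precedence.

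**Where FPG is tested.** SAP 2.4.4.3 places it at step 7 (6 mg) and step 8 (4 mg), the last two.

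**The concern.** SAP version 2 added the mITT because of the early termination and, according to SAP Table 1, clarified the 2.5.4 windows in the same revision. For HbA1c and body weight, the 30-day window matches the 30-day mITT limit. For FPG it does not. A participant can therefore be admitted because the stop was close enough to Week 56, attend the visit and give a fasting sample, and then have that sample set aside in favour of a value that assumes, on average, no change from baseline.

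The reason for the stop is administrative. In SAP 2.4.4 the plan itself regards COVID-related missingness as likely to be missing at random. A sponsor's stopping date has no clearer link to outcome, yet here the filled-in value represents complete loss of benefit.

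At stake is the confirmatory FPG comparison: an attenuated difference, a wider interval, and HbA1c and FPG results that rest on different data from the same visit. No planned analysis would show the effect. The tipping-point, retrieved-dropout, completer and COVID sensitivity analyses in SAP 2.4.4.1 and 2.4.4.1.1 are specified for HbA1c.

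**Working it through.** **The plan's own figure.** SAP 1.3: 300 per arm, SD 1.1%, true difference 0, margin 0.3%, stated power 91%. The standard error is 1.1 × √(2/300) = 0.0898, and 0.3/0.0898 = 3.34. Power is Φ(3.34 − 1.96) = 0.916 (0.915 with the noncentral t). The figure reproduces. It concerns HbA1c and is not in question here.

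**The gap in days.**
- mITT limit: 392 − 30 = Day 362.
- FPG window opens: 392 − 7 = Day 385.
- Visits in the gap: Days 362 to 384, which is 384 − 362 + 1 = 23 days.

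| End-of-treatment visit | HbA1c, weight (30 days) | FPG (7 days) |
|---|---|---|
| Days 362 to 384 | used | missing, imputed around baseline |
| Days 385 to 391 | used | used |

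**Direction of the effect.** Let m_E and m_D be the true mean FPG changes and g_E and g_D the shares in the gap. The imputed change averages 0, so the estimated difference is (1 − g_E)·m_E − (1 − g_D)·m_D.
- Equal shares g: this becomes (1 − g)(m_E − m_D), which is shrinkage towards zero.
- No true difference, m_E = m_D = m: this becomes (g_D − g_E)·m, which is zero only if the shares match. With an assumed mean fall of 2.3 mmol/L, each percentage point of imbalance shifts the difference by 0.01 × 2.3 = 0.023 mmol/L.

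**Size, illustration only.** The documents give no FPG effect, no FPG SD and no number affected, so every FPG input below is an assumption.

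*A. Dilution only:* 300 per arm, standardised difference 0.25, SD unchanged.
- None affected: 0.25/√(2/300) = 3.06; power Φ(3.06 − 1.96) = 86.5%.
- 5% affected: 0.25 × 0.95 = 0.2375; 0.2375/√(2/300) = 2.91; power 82.9%.
- At 5%, the other effect sizes tried give 68.8% to 64.3% (0.20) and 95.7% to 93.7% (0.30).

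*B. Dilution plus added variance:* 250 per arm, difference 0.5 mmol/L, SD 2.2, baseline SD 2.0, mean change 2.3.
- None affected: 0.5/(2.2 × √(2/250)) = 2.54; power 72%.
- 5% affected: the difference is 0.5 × 0.95 = 0.475. The variance is 0.95 × 2.2² + 0.05 × 2.0² + 0.05 × 0.95 × 2.3² = 5.05, plus 0.05 × 2.0² = 0.20 between imputations, giving 5.25. Then 0.475/√(2 × 5.25/250) = 2.32; power 64%.

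The loss at 5% is about 4 points in A and 8 points in B.

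**The case against.** **The neighbouring paragraph may already rescue the value.** If a stop in this band counts as *just before* Week 56, the FPG is mapped to Week 56 and nothing is lost. This stands as a real ambiguity, so the documents do not support a flat statement that the value is always discarded. It does not remove the point. The later paragraph is the more specific one, since it names end-of-treatment visits of early stoppers, Day 392 and FPG. The SAP does not say which rule governs, and the two readings give different FPG analyses from the same data.

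**A short FPG window is a defensible choice.** Protocol 3.1 describes HbA1c as reflecting the previous 120 days, whereas FPG is a single fasting reading. This stands for participants who had already stopped treatment before the termination (third mITT bullet). It is weaker for those whose treatment the termination itself stopped: their reading may still show treatment effect, and the substitute is a no-effect value. Whether a given reading is on treatment depends on the time since the last dose, because the visit is only requested as soon as possible.

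**The consequence is limited.** This is right. FPG is formally tested only after six superiority tests succeed. With similar shares by arm, which randomisation makes likely, the error is conservative. The last on-treatment FPG also stays in the descriptive summaries (SAP 2.4.4.2.2).

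**A head count is tempting but not supported.** A reader might infer one by spreading 900 participants evenly over 12 to 18 months: 23 × 900/547 = 38 to 23 × 900/365 = 57. The documents give no recruitment dates. The count also needs recruitment to have been open in that 23-day slice and everyone to have stopped on 9 September 2020.

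**Conclusion.** The mismatch is real on the text of SAP 2.5.4, 2.3.1.2, 2.4.4.2.2 and 2.4.4.1. It covers only termination-stopped participants whose end-of-treatment visit falls on Days 362 to 384, and only the FPG endpoint. It should be settled before the analysis.

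A reader might infer that all termination-stopped participants lose their FPG value, or that the primary result is at risk. Neither follows: values from Day 385 on are kept, and HbA1c and weight use the 30-day window.

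The number affected and the loss of power cannot be derived from the documents. The 4- to 8-point loss rests on an assumed 5% affected and on assumed FPG inputs. The conservative direction rests on similar shares by arm; with unequal shares the bias can go either way.

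The gap does not depend on the mITT/ITT conflict, because these participants are in both populations. Under ITT, those stopped more than 30 days early would be imputed as well, so that conflict also needs resolving.

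**What to change.** In SAP 2.5.4:

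1. For participants whose treatment the early termination stopped within 30 days of Day 392, use the fasting central-laboratory FPG from the end-of-treatment visit as the Week 56 value, provided it was taken while still on treatment (for example, within one dosing interval of the last dose).
2. Keep 7 days for all others, including participants who stopped treatment before the termination.
3. State that this rule takes precedence over the early-discontinuation paragraph for these visits.
4. Report the 7-day rule as a sensitivity analysis for FPG.

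The cost is a short SAP edit and one extra FPG analysis. The downside is that a few FPG values are taken up to 30 days early, as is already accepted for HbA1c and body weight.
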